3.6.2 Cumulative dose and average daily dose

Cumulative dose for any component of study treatment is defined as the total dose of the medication given during the study treatment exposure.

Average daily dose is defined as [Cumulative dose (mg) / Number of dosing days]; drug free day(s) are not counted as dosing days.

Cumulative dose and average daily dose will be summarized using descriptive statistics by treatment arm for each component of study treatment. Patients with no exposure to the study treatment component will be excluded from the corresponding summary.

3.6.3 Dose intensity and relative dose intensity

Dose intensity (DI) for ribociclib/placebo for patients with non-zero duration of exposure to ribociclib/placebo is defined as follows:

$DI \text{ (mg / day)} = \text{Cumulative dose (mg)} / \text{adjusted duration of exposure to ribociclib/placebo (day)}$,

where *adjusted* duration of exposure (days) to ribociclib/placebo is the number of ribociclib /placebo dosing days a patient would be expected to have received per protocol, given their duration of exposure. Since ribociclib /Placebo follows a 3 weeks on, 1 week off schedule, the adjusted duration of exposure to ribociclib/placebo is the duration of exposure to ribociclib/placebo minus the planned off days for ribociclib /placebo. The adjusted duration of exposure to ribociclib/placebo (in days) is therefore $21 * (\# \text{ completed } 28 \text{ day period}) + \min(21, \text{duration of last incomplete cycle})$.

For example, if the duration of exposure to ribociclib/placebo is 66 (corresponding to two cycles and 10 days) days, then the adjusted duration of exposure to ribociclib/placebo is $21*2+10=52$ days. If the duration of exposure to ribociclib/placebo is 108 days (corresponding to three cycles and 24 days), then the adjusted duration of exposure is $21*3+21=84$ days.

Specifically, let D1 represent the duration of exposure to ribociclib/placebo as defined above. Then the adjusted duration of exposure is defined as

$D=21*[D1/28] + \min(21, D1-28*[D1/28])$ days,

where [x] stands for the integer part of x. In this equation [D1/28] is the number of completed cycles, and $D1-28*[D1/28]$ is the additional number of days in the last, incomplete cycle (if any). For example, if D1=30 then [D1/28]=1, $D1-28*[D1/28]=2$, and D=23. If D1=7 then D=7; if D1=22 then D=21; if D1=28 then D=21, etc.

Planned dose intensity (PDI) is defined as the assigned dose by unit of time planned to be given to patients as per protocol. The PDI for ribociclib/placebo is displayed in [Table 3-1](#). Note that DI will also be calculated and DI for ribociclib/placebo will be reported in the units displayed in [Table 3-1](#), whereas duration of exposure itself will be summarized in months.

Table 3-1 Planned dose intensity

Medication	PDI (dose unit/unit of time)
ribociclib /placebo	600 mg/day (3 weeks on 1 week off)

Ribociclib/placebo relative dose intensity (RDI) is defined as:

$$\text{RDI} = \text{DI (dosing unit / unit of time)} / \text{PDI (dosing unit / unit of time)}.$$

Fulvestrant RDI is defined as:

RDI = actual cumulative dose / planned cumulative dose, where planned cumulative dose is defined as 500* (# completed D1 in a 28-days cycle) and added by 500 mg if patients completed C1D15.

DI for ribociclib/placebo and RDI for ribociclib/placebo and fulvestrant will be summarized separately for each of the study treatment component.

3.6.4 Dose reductions, interruptions and delays

The number and percentage of patients with dose reductions, interruptions or delays, and the reasons, will be summarized by treatment arm.

Interruption: An interruption is defined as a 0 mg dose given on one or more days during the period where a patient is not on the “off” part of a treatment cycle, after which > 0mg dose resumes. For patients who had dose interruption checked but never resumed non-zero dose, the dose interruption will not be counted. For example, in the sequence of 600 mg – 0mg (dose break) -0mg (dose interruption) – 0 mg (dose permanently discontinuation) the 0mg (dose interruption) will not be counted as dose interruption. Interruptions will be summarized for each component of the study treatment. **Delay:** A special case of ribociclib/placebo interruption occurs at the start of a new cycle, after a planned rest period. It will be determined based on ribociclib / placebo dose administration record where a planned dose break is followed by a dose interruption. Such instances will be identified as a subset of the interruptions and will be summarized separately as dose delays.

Reduction: A reduction is defined as a decrease from the previous non-zero dose to another non-zero dose less than protocol planned dose, even if this decrease has been directly preceded by an interruption. For example, in the sequence of ribociclib 600mg – 0mg – 400mg, the 400mg dose will be counted as a reduction.

If due to dosing error, a patient took a dose during the dosing break with a dose that is lower than the previous dose, this will not be considered as dose reduction. For example, a patient took 600 mg from day 1-21, and mistakenly took 200 mg per day on day 22-28 which is supposed to be a dosing break. The patient resumed 600 mg dosing on day 29. This will not be considered as dosing reduction.

Dose reductions and interruptions will be tabulated separately. Dose escalations are not allowed according to the protocol and will not be counted in these summaries.

Missing data: If dose is recorded but frequency is missing or entered as ‘none’, it is assumed that the study drug was taken as per-protocol.

3.6.5 Discontinuation of study treatment components

The reasons for discontinuation of ribociclib/placebo will be summarized by treatment arm, based on the information on the ribociclib/placebo DAR CRF for patients who have the “dose permanently discontinued” box checked.

Partial discontinuation: A partial discontinuation is defined as the event when the last non-zero dose of ribociclib/placebo is more than 21 days before the last non-zero dose of fulvestrant when the permanent discontinuation checkbox is checked in the ribociclib/placebo DAR page.

Partial Discontinuation of ribociclib/placebo will be summarized by treatment

3.7 Concomitant and post-treatment therapy

Concomitant therapies

Concomitant therapy is defined as all interventions (therapeutic treatments and procedures) besides the study treatment that were administered to a patient, coinciding with the study assessment period (even if started before the study assessment period).

Concomitant medications will be coded using the World Health Organization (WHO) Drug Reference Listing (DRL) dictionary that employs the WHO Anatomical Therapeutic Chemical (ATC) classification system.

Concomitant medications will be summarized by lowest ATC class, preferred term and treatment arm. These summaries will include:

1. medications starting on or after the start of study treatment but no later than 30 days after last dose of study treatment, and
2. medications starting prior to the start of study treatment and continuing after the start of study treatment.

All concomitant therapies will be listed. Any concomitant therapies starting and ending prior to the start of study treatment or starting more than 30 days after the last date of study treatment will be flagged in the listing.

[figure not shown]
The safety set will be used for all concomitant medication tables and listings.

Concomitant medications that have the potential to impact some specific analyses (e.g. PK, efficacy or safety analyses) will be identified prior to database lock. Separate summaries of these concomitant medications will be produced using the appropriate analysis set (e.g. FAS for those potentially affecting efficacy).

- Strong inhibitors or inducers of CYP3A4/5, substrates of CYP3A with a narrow therapeutic window, medications with a known risk of QT prolongation and other prohibited medications described in [Section 2.4](#) will be identified. They will be tabulated by ATC class and preferred term.
- Any anti-neoplastic therapy administered concomitantly with study treatment will be listed based on their identification through the protocol deviation process.

Post treatment anti-neoplastic therapy

Anti-neoplastic therapies after discontinuation of study drug will be listed and tabulated by ATC class, preferred term and treatment arm by means of frequency counts and percentages using the FAS. In addition, 1st line and 2nd line anti-neoplastic medications after discontinuation of study drug will be summarized by medication type, e.g. hormonal therapy, chemotherapy, etc. The medication type will be determined by clinical review.

3.8 Efficacy evaluation

The efficacy endpoints based on the tumor assessments will be derived according to the RECIST guideline version 1.1 (see [\[Appendix 2 of the Clinical Study Protocol\]](#) for details). The tumor endpoint derivation is based on the sequence of overall lesion responses at each assessment/time point. However, the overall lesion response at a given assessment/time point may be provided from different sources as illustrated in [Table 3-2](#).

Table 3-2 Sources for overall lesion response

Source 1	Investigator (local radiology) reported overall lesion response
Source 2	Novartis-calculated overall lesion response based on raw (i.e. individual lesion) measurements from investigator (local radiology)
Source 3	Final BIRC reported overall lesion response

The primary efficacy analysis will be based on the investigator/local radiology review. The investigator reported overall lesion response at each assessment/time point (Source 1 in [Table 3-2](#)) will be used to derive the efficacy endpoints.

The overall response at each assessment will also be calculated using the raw lesion measurements (Source 2 in [Table 3-2](#)). The calculated responses will be listed along with the responses given by the investigator. As a sensitivity analysis, PFS based on calculated overall lesion response (Source 2 in [Table 3-2](#)) will also be summarized. Tumor assessment data based on BIRC will be used for supportive efficacy analysis. The BIRC comprises of two independent radiologists and an adjudicator. The BIRC-reported overall tumor response data will be used to derive the supportive BIRC-based endpoints. Data from the two independent central readers will be listed together with the adjudication. Differences in overall responses between local radiology (Source 1) and central radiology (Source 3) will be listed

3.8.1 Primary efficacy

PFS based on local radiology assessment is the primary efficacy variable in this study. PFS is defined as the time from the date of randomization to the date of the first documented disease progression or death due to any cause. If a patient has not progressed or died at the analysis cutoff date, PFS will be censored at the time of the last adequate tumor assessment before the cut-off date. Definitions and further details on PFS can be found in [\[Appendix 2 of the study protocol\]](#).

Discontinuation due to disease progression (collected on the ‘End of treatment’ and ‘End of post treatment follow up’ disposition page) without supporting objective evidence (as defined in [Section 2.5.2](#)) satisfying progression criteria per RECIST will not be considered disease progression for PFS derivation.

3.8.1.1 Primary analysis

The primary analysis of PFS will be based on the local radiological assessments (Source 1 in [Table 3-2](#)). The analysis will be performed on the FAS and will use the default censoring and event date options from [[Table 14-7 of study protocol Appendix 2](#)], i.e. event/censoring rules will be based on options A(1), B(1), C1(1), C2(1), D(1), E(1), and F(1) (summarized in [Table 3-3](#)). In particular, PFS will be censored at the last adequate tumor assessment if a patient didn’t have an event or the event occurred after two or more consecutive missing tumor assessments (see [Section 2.5.5](#)). For the primary analysis, in this study, PFS will not be censored if a new antineoplastic therapy is started; instead, an ITT approach will be used for the purposes of PFS derivation , i.e. option F(1) in [[Table 14-7 of protocol Appendix 2](#)] will be used. A sensitivity analysis will be performed censoring PFS at the last adequate tumor assessment prior to start of new antineoplastic therapy, i.e. using option F(2). Discontinuation of study treatment (for any reason) will not be considered as a reason for censoring.

Table 3-3 Outcome and event/censor dates for primary PFS analysis

Situation	Date	Outcome
No baseline assessment	Date of randomization *	Censored
Progression or death at or before next scheduled Assessment	Date of progression (or death)	Progressed
Progression or death after exactly one missing assessment	Date of progression (or death)	Progressed
Progression or death after two or more missing assessments	Date of last adequate assessment prior to missed assessment	Censored
No progression (or death)	Date of last adequate assessment	Censored
New anticancer therapy given prior to protocol defined progression	Ignore the new anticancer therapy and follow situations above	As per above situations
Treatment discontinuation due to ‘Disease progression’ without documented progression, i.e. clinical progression based on investigator claim	Ignore clinical progression and follow situations above	As per above situations

*The rare exception to this is if the patient dies no more than D2 days (see [Section 2.5.5](#) for definition) after randomization, in which case this is a PFS event at the date of death.

3.8.1.2 Hypothesis and test statistic

The primary efficacy analysis will be the comparison of PFS between the two treatment arms using a stratified (strata based on IRT data) log-rank test at one-sided 2.5% level of significance.

Assuming proportional hazards model for PFS, the following statistical hypotheses will be tested to address the primary efficacy objective:

$$H_{01}: \theta_1 \geq 0 \text{ vs. } H_{a1}: \theta_1 < 0$$

where θ_1 is the log-hazard ratio (fulvestrant+ ribociclib arm vs. fulvestrant + placebo arm) of PFS.

3.8.1.3 Kaplan-Meier estimates

The survival distribution of PFS will be estimated using the Kaplan-Meier method. The results will be plotted graphically (Kaplan-Meier curves) by treatment arm. The plots will display the number of patients at risk at equidistant time points. The median, 25th and 75th percentiles for PFS for each treatment arm will be provided with associated 95% confidence intervals. The survival probabilities at 2- month intervals, and the associated 95% confidence intervals will be summarized by treatment arm. Kaplan-Meier estimates will be obtained using PROC LEFEST with method=KM option in SAS. The loglog (double log) option available within PROC LIFEST will be used to compute the confidence intervals.

Hazard Ratio

The PFS hazard ratio with two-sided 95% confidence interval will be derived from the stratified Cox proportional hazards model. In this analysis the baseline hazard function will be allowed to vary across strata. SAS PHREG procedure with ties=EXACT option will be used to carry out this analysis in which the model statement will include treatment arm variable as the only covariate and the STRATA statement will include the stratum information as obtained via IRT.

3.8.1.4 Sensitivity and supportive analyses of the primary endpoint PFS

Audit-based BIRC assessment of PFS

PFS assessed by Blinded Independent Review Committee (BIRC) will be used as a supportive analysis of the primary endpoint.

For studies with PFS based on local radiology assessment as the primary endpoint, PFS assessed centrally has generally been used as a secondary or supportive analysis of the treatment effect observed in the primary efficacy analysis. Although 100% central review of scans has been performed in many trials, there is a growing body of evidence that an audit based approach for central evaluation is sufficient ([Zhang et al, 2012](#), [FDA ODAC 2012](#)).

An audit (sample) based approach will therefore be implemented for the BIRC assessment of PFS, whereby all assessments for a randomly selected subset of randomized patients will be assessed by BIRC. An independent random sampling process, implemented by the third party IRT vendor, will select approximately 40% of randomized patients. This random allocation

will be stratified by randomized treatment arm and the strata used for the randomization of patients to treatment arms.

The distribution of PFS based on the audit BIRC sample will be estimated using the Kaplan-Meier method. The median along with two-sided 95% confidence interval (CI) will be presented by treatment group. A Kaplan-Meier figure will also be displayed. A stratified Cox regression will be used to estimate the hazard ratio (HR), along with two-sided 95% CI based on the audit BIRC sample.

In order to determine whether a 100% BIRC review should be conducted, two additional methods will be used to summarize the data from the sample-based BIRC assessment.

1. NCI method: The NCI (National Cancer Institute) method ([Dodd et al. 2011](#)) uses an auxiliary variable estimator of the log-hazard ratio that combines information from patient-level investigator assessments from all patients (in the FAS) and the BIRC assessment of patients randomly selected for central review (see [Section 4.6](#) for methodology details). This estimate and its one-sided 95% CI will be provided. The NCI method is used for the audit sample size determination (see [Section 3.16](#)) and summary of treatment effect for the supportive BIRC assessment.
2. PhRMA method: The data from the BIRC assessment generated following the sampling scheme as above will also be summarized using the method proposed by [Amit et al. 2011](#), referred to as the PhRMA (Pharmaceutical Research and Manufacturers of America) method, based on the early discrepancy rate (EDR) and late discrepancy rate (LDR). The EDR quantifies the frequency with which the investigator declares progression early relative to BIRC within each arm as a proportion of the total number of investigator assessed PDs. The LDR quantifies the frequency that the investigator declares progression later than BIRC as a proportion of the total number of discrepancies within the arm (see [Section 4.6](#) for further details). If the distribution of discrepancies is similar between the arms this suggests the absence of evaluation bias favoring a particular arm. With this approach, the differential discordance (DD) of the early discrepancy rate (EDR) and late discrepancy rate (LDR) between the two arms will be estimated as the rate on the ribociclib+fulvestrant arm minus the rate on the placebo+fulvestrant arm. The EDR and LDR results will also be summarized by treatment arm.

The following thresholds based on the NCI and PhRMA methods will be used to define the trigger for a full BIRC review:

- If the upper-bound of the one-sided 95% confidence interval for BIRC-based log-hazard ratio exceeds zero (i.e. $HR > 1$) based on the NCI method
- and/or
- If $\geq 15\%$ differential discordance is observed in EDR or LDR based on the PhRMA method.

A full BIRC review will only be considered if the primary endpoint is statistically significant. In the event of a full BIRC read of all patients' imaging data, all analyses based on BIRC assessment will be repeated including all randomized patients, with the exception of the auxiliary variable estimate (NCI method) described above.

Sensitivity analyses and further supportive analyses

As a sensitivity analysis to assess the impact of stratification, the two treatment groups will be compared using an unstratified log-rank test. The hazard ratio together with associated 95% confidence interval obtained using the unstratified Cox regression model will also be presented.

The primary efficacy analyses; i.e. the stratified log-rank test, Kaplan-Meier estimates, estimate of the median PFS along with 95% confidence interval, and hazard ratio obtained using the Cox proportional hazards model, will be repeated (as appropriate) based on the data obtained:

1. Using the investigator/local assessments (Source 1 in [Table 3-2](#)) on the PPS and using the same conventions as for the primary analysis if the primary analysis is found to be statistically significant and if the PPS/FAS are different.
2. Using investigator/local assessment (Source 1 in [Table 3-2](#)) on the FAS and taking the event whenever it occurs - even after two or more consecutive missing tumor assessments. The following options from [[Table 14-7 of Study Protocol Appendix 2](#)] will be used: A(1), B(1), C1(1), C2(3), D(1), E(1) and F(1). In the summary table, this approach is referred as 'Actual event PFS analysis'
3. Using investigator/local assessment (Source 1 in [Table 3-2](#)) on the FAS and backdating events occurring after missing tumor assessments. The following options from [[Table 14-7 in Section 3.2.9 of Study Protocol Appendix 2](#)] will be used: A(1), B(1), C1(2), C2(2), D(1), E(1), and F(1). In the summary tables, this approach is referred as 'Backdating PFS analysis'.
4. Using investigator/local assessment (Source 1 in [Table 3-2](#)) on the FAS and censoring PFS at the last adequate tumor assessment before the start of any new antineoplastic therapy excluding palliative radio-therapy.

A stratified multivariate Cox regression model will be fitted to evaluate the effect of other baseline demographic or disease characteristic on the estimated hazard ratio. This model will include the treatment arm and the following key prognostic factors as covariates: age (≥ 65 vs < 65), prior chemo therapy in (neo)adjuvant setting (yes vs no), ECOG performance status (0 vs. 1), and bone only lesion at baseline (yes or no). In addition, stratified multivariate cox models will be fitted including the treatment arm and each of these prognostic factors individually, including treatment by factor interaction, to explore the relationship between each factor and treatment. Further supportive analyses will include:

- Stratified Cox regression using derived local radiology assessment (source 2 in [Table 3-2](#)). No p-value will be presented.
- Number of patients and number of events by treatment arm within each stratum will be presented along with the hazard ratio for treatment effect obtained using the Cox proportional hazards regression with corresponding confidence intervals. No p-values will be presented for this analysis. K-M plots of survival distributions will be presented by stratum.

- If there is a high rate of discrepancy between the strata classifications constructed using the eCRF data and those obtained from the IRT, a supportive analysis will be performed in which a stratified Cox regression model will be used to estimate the treatment hazard ratio and the associated 95% confidence interval based on the CRF-derived strata. No other inferential statistics will be provided.
- Number of patients with a PFS event and number of patients censored for the PFS analysis will be summarized. In addition, a summary of reasons for PFS censoring will be provided by treatment arm based on the reasons defined in [Section 2.5.5](#). These summaries on censoring reasons will be produced for PFS as per local investigator radiology and BIRC assessment.
- Comparison of PFS event type/censor between local investigator radiology review and BIRC assessment
- If the primary analysis for PFS is statistically significant, the treatment effect for patients treatment naïve in the metastatic setting and for patients who received up to 1 line of treatment for advanced disease (groups A and B as defined in section 1.1) based on CRF data will be evaluated using unstratified Cox regression models. The hazard ratio with 95% CI will be displayed for each subgroup and Kaplan-Meier estimates will also be summarized.

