## 2.2 Rationale for the study design

This is a randomized, placebo-controlled two-arm study with the objective to evaluate the efficacy and safety of adding ribociclib to fulvestrant in men and postmenopausal women with advanced breast cancer. The randomized, double-blind, placebo controlled, multicenter, parallel group design is the gold standard for phase III trials as it minimizes allocation bias, balancing both known and unknown prognostic factors in the assignment of treatments.

A randomization ratio (ribociclib+fulvestrant vs placebo+fulvestrant) of 2:1 is selected, since the efficacy and safety of fulvestrant is well characterized, a 2:1 randomization will allow a better evaluation of efficacy and safety of the ribociclib+fulvestrant combination. Randomization will be stratified by the following factors (see [Section 4.1](#) for further details):

1. Lung or liver metastases (yes versus no)
2. Previous endocrine therapy

The stratification factors are selected because of their well-recognized prognostic value.

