#### 10.4.4 Supportive analyses

As a sensitivity analysis, the distribution of PFS will be compared between the treatment groups using an unstratified log-rank test and the hazard ratio along with the associated 95% confidence interval resulting from an unstratified Cox model will be presented.

The primary analysis for PFS may be repeated with data based on PPS if the primary analysis is statistically significant. Other sensitivity analyses may be performed such as (1) including PFS events even if the events are recorded after two or more missed assessments, (2) backdating events occurring after missing tumor assessments.

Subgroup analyses will be performed on each level of stratification factors if the primary analysis is significant. The analysis will include Kaplan-Meier summaries and estimation of hazard ratios from un-stratified Cox regression models. Additional subgroup analyses to assess the homogeneity of treatment effect based on demographic and baseline disease characteristics

may be performed; details about the subgroups to be included will be provided in the study analysis plan.

Patterns of censored data will be examined by the treatment groups using descriptive statistics (the numbers of censored patients and reasons for censoring).

PFS assessed by BIRC will serve as supportive evidence of the primary end point. Two methods will be used to summarize the data from the BIRC assessment. The NCI (National Cancer Institute) method (Dodd et al. 2011), uses an auxiliary variable estimator of the log-hazard ratio that combines information from patient-level investigator assessment from all patients and the BIRC assessment of patients randomly selected for central review. This estimate and its one-sided 95% CI will be provided. Details of the audit sample size calculation for the BIRC assessment are provided in [Section 10.8](#). The NCI method will be used for audit sample size determination and summary of treatment effect (HR, 95% confidence intervals) based on the supportive BIRC assessment.

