**Table 10-2 Probability of Study Outcomes under various true Hazard Ratios**

True Hazard Ratio	% statistical significance*
0.5	100
0.6	99.7
0.67	96
0.7	91
0.8	53
0.9	16
A total of 660 patients will be enrolled with exponential dropout hazard rate 0.0105 (about 10% drop out rate) *: Based on 10,000 simulations using EAST 6.3	

The primary objective of the study is to compare investigator assessed PFS between arms in the overall population (both 1st line and 2nd line patients). If the primary analysis is statistically significant, treatment effect will be evaluated in 1st and 2nd line patients separately. Based on the estimated median PFS and proportion of patients in 1st line and 2nd line respectively, it is expected that the accumulation of events in 1st line will be slower than 2nd line patients. To ensure enough information coming from 1st line patients, the final analysis will be done after approximately 125 events in the first line patients or approximately 364 events in both arms whichever comes later.

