1.1 Study design

This is a randomized, phase III, double blind, placebo controlled, international study to determine the efficacy and safety of treatment with fulvestrant with ribociclib versus fulvestrant with placebo in men and postmenopausal women with HR+, HER2-negative advanced breast cancer. This study will consist of 4 phases: screening (up to 28 days), randomized treatment, post-treatment efficacy follow-up, and post-treatment survival follow-up.

Approximately 660 patients will be randomly assigned to one of the following treatment arms in a 2:1 ratio.

- Experimental arm: fulvestrant (500 mg intramuscular [as two 5 mL injections] on Cycle 1 Days 1 and 15 (C1D1 and C1D15), and on CnD1 thereafter) + ribociclib (600 mg by mouth once daily for three weeks followed by one week break, in a 28-day cycle)
OR
- Control arm: fulvestrant (500 mg intramuscular [as two 5 mL injections] on Cycle 1 Days 1 and 15 (C1D1 and C1D15), and on CnD1 thereafter) + ribociclib placebo (by mouth once daily for three weeks followed by one week break, in a 28-day cycle)

Randomization will be stratified by the following factors:

1. Lung or liver metastases: (yes vs no)
2. Previous endocrine therapy (A vs B) according to the following definition:

A) Patients treatment naïve in the metastatic/advanced disease setting:

- i- whose disease relapsed >12 months after completion of (neo)adjuvant endocrine therapy with no subsequent treatment for advanced/metastatic disease,

OR

- ii- with de-novo advanced/metastatic disease (no prior exposure to endocrine therapy).

- B) Patients who received up to 1 line of treatment for metastatic/advanced disease:
- i- whose disease relapsed on or within 12 months from completion of (neo) adjuvant endocrine therapy, with no subsequent treatment for advanced/metastatic disease,
OR
 - ii- whose disease relapsed > 12 months from completion of (neo) adjuvant endocrine therapy, and progressed on or after subsequent endocrine treatment for advanced/metastatic disease,
OR
 - iii- with advanced/metastatic disease at the time of diagnosis that progressed on or after endocrine therapy for advanced/metastatic disease with no prior (neo) adjuvant treatment for early disease.

[figure not shown]
PFS, as assessed by the local radiologists/investigators and using RECIST 1.1 criteria will be the primary endpoint. PFS as assessed through audit-based blinded independent review committee (BIRC) will be a supporting end point for primary analysis.

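### First-line and second-line PFS hazard ratios come only from unstratified Cox models that leave out lung/liver metastases, so they may sit slightly nearer 1 than the stratified overall hazard ratio

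*SAP*

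**What the plan says.** Randomisation used two factors: "Lung or liver metastases: (yes vs no") and previous endocrine therapy, group A or B (SAP 1.1). SAP 3.16 equates A and B with first and second line. Protocol 2.2 gives the reason for the choice: "The stratification factors are selected because of their well-recognized prognostic value".

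The primary comparison is a "stratified (strata based on IRT data) log-rank test" (SAP 3.8.1.2), and the overall hazard ratio comes from a Cox model with the same IRT strata (SAP 3.8.1.3).

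The line-specific analysis is conditional on the primary result. Protocol 10.8 states: "If the primary analysis is statistically significant, treatment effect will be evaluated in 1st and 2nd line patients separately". SAP 3.8.1.4 sets the method: groups A and B "based on CRF data will be evaluated using unstratified Cox regression models". On output it says "The hazard ratio with 95% CI will be displayed for each subgroup", together with Kaplan-Meier estimates. Protocol 10.4.4 likewise specifies "estimation of hazard ratios from un-stratified Cox regression models" for each level of the stratification factors. The visible text names no stratified model for either line.

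**The concern.** Inside a line group, previous endocrine therapy is fixed by definition, apart from any IRT/CRF disagreement. Lung/liver metastases still varies and was one of the two randomisation factors. The overall hazard ratio is conditional on it and the line-specific hazard ratios are not, so the figures a reader will compare are on different scales. For the whole population, SAP 3.8.1.4 treats the unstratified model as a sensitivity analysis of the effect of stratification. For the two lines it is the only model named.

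The first-line estimate is more than a routine subgroup row. Amendment 2 dropped the efficacy interim partly because first-line events might be too few at that point, and Protocol 10.8 and SAP 3.16 delay the PFS analysis until about 125 first-line events have accrued. An estimate that sets the timing of the analysis deserves a model that matches the primary one.

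**Working it through.** **Plan's own figure.** Schoenfeld power = Φ(√(d·p(1−p))·|ln HR| − 1.960), with d = 364 events, p = 2/3 (2:1 allocation) and HR = 0.67 (Protocol 10.8, SAP 3.16). √(364 × 2/9) = 8.994; 8.994 × 0.4005 = 3.602; 3.602 − 1.960 = 1.642; Φ(1.642) = 0.950. This reproduces the stated 95%. The documents give no power for either line.

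**Precision of the line-specific estimates.** From the same sections, first line is 0.40 × 660 = 264 patients with about 125 events. Second line is 0.60 × 660 = 396 patients with 364 − 125 = 239 events by subtraction. SE(ln HR) = 1/√(d × 2/9), which is 0.190 for first line and 0.137 for second line. The 95% interval is 0.67 × exp(±1.96 × SE): 0.46 to 0.97 and 0.51 to 0.88.

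**Effect of leaving the factor out.** 4,000 trials were simulated per setting and both models were fitted to each trial.
- From the documents: control medians 18 and 6.5 months, uniform accrual over 19 months, dropout hazard 0.0105 (taken as per month), conditional HR 0.67, 2:1 allocation within each lung/liver level.
- Assumed, because the documents give neither: a hazard ratio for lung/liver metastases of 1.25 to 3, and a prevalence of 50%.
- Each line was cut at its own event count, so the two lines do not share a calendar date.

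Average HR is the exponential of the mean log HR. The last column is ln(unstratified/stratified) divided by the mean unstratified SE (0.184 to 0.185 in first line, 0.134 in second line).

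| Line | Factor HR | Unstratified | Stratified | Difference | Shift in SEs |
|---|---|---|---|---|---|
| First | 1.25 | 0.6693 | 0.6678 | 0.0015 | 0.01 |
| First | 1.5 | 0.6714 | 0.6676 | 0.0038 | 0.03 |
| First | 2 | 0.6804 | 0.6695 | 0.0109 | 0.09 |
| First | 3 | 0.6989 | 0.6733 | 0.0256 | 0.20 |
| Second | 1.25 | 0.6720 | 0.6705 | 0.0015 | 0.02 |
| Second | 1.5 | 0.6738 | 0.6686 | 0.0052 | 0.06 |
| Second | 2 | 0.6842 | 0.6690 | 0.0152 | 0.17 |
| Second | 3 | 0.7032 | 0.6674 | 0.0358 | 0.39 |

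For example, first line at 2: ln(0.6804/0.6695) = 0.016, and 0.016/0.184 = 0.09.

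**Prevalence.** In first line with a factor HR of 2, 30% prevalence gives 0.679 against 0.668 and 70% gives 0.677 against 0.669, close to the 50% result.

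**Simulation error.** The error on an average log HR is 0.184/√4,000 = 0.003 in first line, which is why the stratified averages scatter around 0.67. The differences are more precise because both models see the same trials. With a non-prognostic factor (HR 1) the two first-line averages agree, 0.6734 and 0.6733.

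**Cost in precision.** At a factor HR of 2, the mean first-line SE goes from 0.1843 to 0.1850, a rise of 0.4%. The largest rise is in second line at 3, from 0.1342 to 0.1352, or 0.7%.

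**The case against.** A reader might infer that the plan loses power. The simulation does give notional rejection rates: at a factor HR of 2 in first line, 55.5% unstratified against 58.9% stratified at one-sided 2.5%. But that test does not exist in the plan. The visible analysis reports an interval and curves, with no p-value, alpha or power statement, and the primary test stays stratified. The objection stands in full.

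A reader might also call the shift bias. Treatment is randomised, so the unstratified hazard ratio is not confounded. It estimates a marginal quantity where the stratified model estimates a conditional one. When the true hazard ratio is below 1 the shift works against ribociclib. This stands too, but it leaves the mismatch of scale with the overall hazard ratio.

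Related output is already planned in SAP 3.8.1.4: hazard ratios within each randomisation stratum and an unstratified overall hazard ratio. These help only in part. With four strata (SAP 4.2.3), the first describes single cells and gives no lung/liver-adjusted figure per line. The second drops previous endocrine therapy as well as lung/liver metastases.

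Using one unstratified method for every subgroup is a defensible convention and breaks no rule in the documents. The SAP's contents list also has blacked-out entries between 3.14.3 and 3.16, and its dedicated subgroup section is not in the visible text, so a stratified version may exist there.

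Finally, the line groups are built from CRF data, so they need not be exact unions of IRT strata. That is a fair point and affects how the fix is written.

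**Conclusion.** The point holds as a minor inconsistency in a supportive analysis. In the visible text, both line-specific hazard ratios omit a randomisation factor that the protocol calls prognostic and that the overall hazard ratio accounts for. The resulting shift toward 1 is negligible at a factor hazard ratio of 1.5 and about 0.01 (first line) to 0.015 (second line) at 2. At 3 it is about 0.026 and 0.036, still well inside the intervals.

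These sizes rest on the assumed prognostic strength and prevalence of lung/liver metastases, proportional hazards, and a common conditional hazard ratio of 0.67. The documents call the factor prognostic without saying how strongly, so they cannot settle which row applies. They do not support reading this as a flaw in the primary result or as a line-specific effect that is materially understated.

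**What to change.** Report the first-line and second-line hazard ratios and 95% intervals from Cox models stratified by lung/liver metastases, and keep the unstratified hazard ratios as a sensitivity result. Use the IRT value of the factor, which is the default source under SAP 3.2.1. Repeat with the CRF value as a check, because the line groups are CRF-defined; SAP 3.2.1 already tabulates disagreements between the two sources. If the redacted subgroup section already holds such a model, a cross-reference is enough.

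The change is a free improvement. It takes one stratification term with two levels, uses data already held, raises the standard error by less than 1%, and leaves the primary test, alpha and sample size alone. Protocol 10.4.4 records that the primary PFS analysis has been done and that only descriptive PFS work may follow, so any result added now should be labelled supplementary and post hoc.
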